15.2 Slit-Lamp Biomicroscopy Examination

A slit-lamp biomicroscopy examination of the cornea, conjunctiva, anterior chamber, lens, and lids will be performed at each visit. The results will be graded as clinically significant (CS) or not clinically significant (NCS).

The results will be summarized using the numbers and percentages for each treatment group and for all subjects at each visit for each eye (study eye and fellow eye). Percentages will be based on the numbers of subjects in each treatment group with responses. Shift tables for the slit-lamp biomicroscopy parameters will also be provided comparing each follow-up visit to the baseline. A subject listing of the slit-lamp biomicroscopy parameters will also be produced.

15.1 Dilated Ophthalmoscopy

A dilated ophthalmoscopy examination of the retina, macula, choroid, optic nerve, vitreous humour, and cup/disc ratio will be performed at each visit. Subject listings of dilated ophthalmoscopy results will be produced.

The results will be summarized using the numbers and percentages for each treatment group and for all subjects at each visit for each eye (study eye and fellow eye, if done at the visit). Percentages will be based on the numbers of subjects in each treatment group with responses. Shift tables for the dilated ophthalmoscopy parameters will also be provided comparing each follow-up visit to the baseline.

15.2 Intraocular Pressure

Intraocular pressure will be summarized at each visit, using continuous and discrete summary statistics, including change from baseline and the proportion of study eyes with an increase from baseline in IOP of 10 mmHg or more and the proportion of study eyes with IOP of 30 mmHg or more.

A subject listing of IOP will also be produced. Increase from baseline in IOP of 10 mmHg or more or IOP of 30 mmHg or more will be flagged in the listing.

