3. INVESTIGATIONAL PLAN

3.1 Overall Study Design and Plan

This will be a 6-month (with follow-up, if necessary, to monitor residual implant), open-label, multicenter study evaluating the safety, tolerability, and efficacy of 2 formulations of dexamethasone intravitreal implant, AR-1105, in a single eye of up-to 45 subjects between 18 and 80 years of age with ME secondary to RVO.

Data collected through Month 6 on the safety and tolerability of each formulation, as well as efficacy signals for each subject randomized, will be used to determine which formulation will be selected for further clinical development. Any subject who presents at Month 6 with

[figure not shown]
visible residual implant will be followed until they require retreatment (following the criteria provided for rescue therapy), or until 1 month after the implant is no longer visible or to Month 9, whichever occurs first.

Rescue therapy in the form of standard of care will be offered to any subject who, in the opinion of the investigator, requires additional therapy for their RVO due to lack of efficacy after Month 3/Week 12. Minimum guideline criteria for consideration of rescue are an increase in CRT of 50 μ m and decrease in BCVA of ≥ 7 letters at any time compared to baseline.

In the case of elevated IOP or cataract, investigators should treat the subject according to standard practice. In the case of a cataract, removal should be performed as soon as possible since BCVA could be impacted by the cataract.

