- *Serious adverse event (SAE) or serious suspected adverse reaction (SSAR)*. An AE or SAR is considered “serious” if, in the view of either the Investigator or Sponsor, it results in any of the following outcomes: Death, a life-threatening AE, patient hospitalization or prolongation of existing hospitalization, a persistent or significant incapacity or substantial disruption of the ability to conduct normal life functions, or a congenital anomaly/birth defect. Important medical events that may not result in death, be life-threatening, or require hospitalization may be considered serious when, based upon appropriate medical judgment, they may jeopardize the patient and may require medical or surgical intervention to prevent one of the outcomes listed in this definition. Examples of such medical events include allergic bronchospasm requiring intensive treatment in an emergency room or at home, blood dyscrasias or convulsions that do not result in patient hospitalization, or the development of drug dependency or drug abuse.

Note: In the present study, Investigators are asked to report any loss in BCVA of ≥ 3 lines as a SAE.

- *Unexpected AE or unexpected SAR.* An AE or SAR is considered “unexpected” if it is not listed in the Investigator’s Brochure (IB) ‘Reference Safety Information’ or is not listed at the specificity or severity that has been observed. For example, under this definition, hepatic necrosis would be unexpected (by virtue of greater severity) if the IB referred only to elevated hepatic enzymes or hepatitis. Similarly, cerebral thromboembolism and cerebral vasculitis would be unexpected (by virtue of greater specificity) if the IB listed only cerebral vascular accidents. “Unexpected,” as used in this definition, also refers to AEs or SARs that are mentioned in the IB as occurring with a class of drugs or as anticipated from the pharmacological properties of the drug, but are not specifically mentioned as occurring with the particular drug under investigation.

Note: If an event occurs during the washout period (prior to subject enrollment and the administration of study medication), it should be recorded as an AE.

Note: Any medical condition present prior to administration of the study medication which remains unchanged or improved should not be recorded as an AE at subsequent visits.

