9.5 Primary Safety Assessments and Analyses

The primary safety analysis will summarize ocular and non-ocular treatment-emergent adverse events (TEAEs) using discrete summaries at the subject level by system organ class and preferred term for each treatment group. Ocular TEAEs will be summarized separately for all study and fellow eyes. A TEAE will be defined as occurring after the first dose of study medication. Serious adverse events and treatment-related ocular and non-ocular TEAEs will be summarized similarly. Ocular and non-ocular TEAEs will also be summarized by severity.

Slit lamp biomicroscopy and dilated indirect ophthalmoscopy measures will be summarized at each visit using discrete summary statistics.

Intraocular pressure will be summarized at each visit, using continuous and discrete summary statistics, including change from baseline and the proportion of study eyes with an increase from baseline in IOP of 10 mmHg or more and the proportion of study eyes with IOP of 30 mmHg or more.

Vital signs and safety laboratory data will be summarized at each visit, using continuous summary statistics, including change from baseline.

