2.1 Primary Variables

The primary variables are related to safety and include the following:

- Ocular and non-ocular treatment-emergent adverse events (TEAE)
- Slit lamp biomicroscopy
- Dilated indirect ophthalmoscopy measures
- Intraocular pressure (IOP), including change from baseline and the proportion of study eyes with an increase from baseline in IOP of 10 mmHg or more and the proportion of study eyes with IOP of 30 mmHg or more.
- Vital signs
- Safety laboratory data

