15.1 Adverse Events

An AE is defined as any untoward medical occurrence associated with the use of a drug in humans, whether or not the event is considered drug-related. An AE can therefore be any unfavorable and unintended sign (e.g., an abnormal laboratory finding), symptom, or disease occurring after informed consent form is signed and dated, without any judgment about causality. Any pre-existing medical condition that worsens after first administration of the study medication will also be considered a new AE. The AE reporting period starts from the time the subject signs and dates the informed consent and until 30 days after the subject's last study visit. All Aes will be coded using the MedDRA 21.1.

Treatment-emergent adverse events are defined as any event that occurs or worsens on or after the study treatment is initiated. Adverse events recorded in the eCRF which began prior to treatment will not be included in the summary tables but will be included in the AE data listings.

An overall summary will be presented that includes the number of TEAEs and the number and percentage of subjects who experienced at least one TEAE, by treatment group. This summary will also include breakdowns of TEAEs further categorized as ocular (study eye, fellow eye, and both eyes separately) or non-ocular, serious TEAEs, TEAEs by maximum severity, TEAEs by maximum relationship to study medication, TEAEs by maximum relationship to study procedure, TEAEs by maximum expectedness, number of serious TEAEs, number of subjects with any serious TEAEs, and with TEAEs leading to death.

Additional summaries of TEAEs will be provided showing the number and percentage of subjects who experienced at least one TEAE. These summaries will be presented by system organ class (SOC) and preferred term (PT). Non-ocular TEAEs will be summarized using discrete summary statistics and presented by treatment group at the subject level by SOC and PT. Ocular TEAEs will be similarly summarized at the subject level for study eyes, fellow eyes, and both eyes separately. If a subject reports the same PT multiple times within the same SOC, that PT will only be reported once within that SOC. As with the PT, if a subject reports multiple conditions within the same SOC, that SOC will only be reported once. In the summary, SOC will be listed in ascending alphabetical order; PTs will be listed in order of descending frequency for all subjects within each SOC.

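### The plan's text gives the two IOP threshold proportions visit by visit only; a proportion of study eyes crossing each threshold at any visit through Month 6 would be a cheap addition

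*SAP*

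**What the plan says.** SAP 2.1 lists IOP among the primary safety variables, including "the proportion of study eyes with an increase from baseline in IOP of 10 mmHg or more" and the proportion at 30 mmHg or more. It attaches no time frame to either.

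The time frame comes from the analysis sections. SAP 15.2 (Intraocular Pressure) says "Intraocular pressure will be summarized at each visit, using continuous and discrete summary statistics, including change from baseline and the proportion of study eyes" at or above each threshold. Protocol 9.5 opens the same way: "Intraocular pressure will be summarized at each visit, using continuous and discrete summary statistics". The synopsis safety analysis agrees, and SAP 8.4 sets summaries by treatment group and, where appropriate, by visit.

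SAP section 20 lists one IOP table (14.3.18), by title only. SAP 15.2 adds for the subject listing that "Increase from baseline in IOP of 10 mmHg or more or IOP of 30 mmHg or more will be flagged in the listing".

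Adverse events are handled cumulatively, per subject and preferred term: "Ocular TEAEs will be similarly summarized at the subject level for study eyes, fellow eyes, and both eyes separately".

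Protocol 3.1 provides that "In the case of elevated IOP or cataract, investigators should treat the subject according to standard practice". It also says that "Data collected through Month 6 on the safety and tolerability of each formulation", together with efficacy signals, will be used to decide which formulation goes forward.

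**The concern.** The protocol's Introduction names raised IOP as a risk of both the implant and its steroid content, and safety is the primary objective. The natural question for each formulation is how many treated eyes crossed a threshold at some point in six months. A table of by-visit percentages does not answer it. An eye over the threshold at Month 2, treated, and back below it at Month 3 appears in one row only. Six eyes that cross once each at different visits can produce lower rows than three eyes that stay high for three visits.

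The plan's sample-size statement is itself about incidence per subject over the study, which an any-visit proportion matches and a by-visit proportion does not.

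At stake is how clearly a primary safety variable reads when the two formulations are compared. No data would be lost.

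**Working it through.** **Inputs.** 20 evaluable subjects per group (SAP section 5). Seven scheduled post-injection visits through Month 6 in the randomized phase: Day 8 and Months 1 to 6 (Protocol 3.3), with IOP checked at each (SAP Table 2). No visits are assumed missing. The number of affected eyes and the duration of rises are not in the documents; those used below are assumptions.

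**1. The plan's own figure.** No figure is stated for the IOP proportions. The only related one is the 13.9% bound for an event not seen in 20 subjects: 1 − 0.05^(1/20) = 0.139. It reproduces as a one-sided exact 95% bound.

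**2. What by-visit rows can and cannot fix.** If r is the row of counts by visit, the number of eyes ever affected lies between max(r) and min(20, sum of r). Conversely, if k eyes are ever affected, the highest single-visit count (the peak) lies between k/7 rounded up and k. For k = 6 (30%), the peak can be 1/20 to 6/20.

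**3. How far apart the two are likely to be.** Take k = 6, with onset equally likely at each of the seven visits, and enumerate all 7^6 = 117,649 onset patterns. Rises that would run past Month 6 are cut off there.

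| Each rise lasts | Mean peak, of 20 | As % |
|---|---|---|
| 1 visit | 2.28 | 11% |
| 2 visits | 3.23 | 16% |
| 3 visits | 3.96 | 20% |
| to Month 6, all eyes | 6 | 30% |

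In the one-visit case a peak of 1 needs six different visits: 7!/1! = 5,040 patterns, and 5,040/117,649 = 4.3%. That extreme is therefore unlikely. A peak of 2 has probability 66.9% and a peak of 3 has 25.3%.

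**4. Can the order of two formulations change?** Constructed rows of eyes over a threshold at Day 8 and Months 1 to 6:

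- A = 0, 2, 2, 1, 1, 0, 0. Eyes ever affected: 2 to 6.
- B = 0, 3, 3, 3, 0, 0, 0. Eyes ever affected: 3 to 9.

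If A is six different eyes and B is the same three eyes, the peak favours A (2/20 = 10% against 3/20 = 15%). The any-visit proportion favours B:

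- A: 6/20 = 30%, exact 95% CI 11.9% to 54.3%.
- B: 3/20 = 15%, exact 95% CI 3.2% to 37.9%.

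Fisher's exact test of 6/20 against 3/20 gives p = 0.45. The reversal is possible arithmetically, but these data would not distinguish the formulations.

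**5. Why the any-visit window must stop at Month 6.** Only subjects with visible residual implant attend Months 7 to 9 (Protocol 7.4), so they have up to 10 scheduled chances to cross instead of 7. With an assumed independent 5% chance per visit, 1 − 0.95^7 = 30% and 1 − 0.95^10 = 40%. Without a cutoff, the formulation that stays visible longer would look worse simply because it is observed for longer.

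**The case against.** The strongest reply is that the information is already available. Both thresholds are flagged in the subject listing, and with about 20 eyes per group anyone can count them. The SAP introduction allows supplementary analyses. The primary safety analysis in Protocol 9.5 is the TEAE summary, which is cumulative; all adverse events must be documented, and Protocol 6.8.4 names increased IOP among the events expected. SAP 2.1 lists several classes of safety variable, so IOP is one of many. Table shells are not in the documents, so Table 14.3.18 might contain an overall row. The ranking example is constructed.

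Most of this stands, and it limits the weight of the point. It does not remove it. A hand count from a listing is not a planned proportion by formulation. TEAE counts rest on investigator reporting rather than on the two thresholds. The protocol sets a numeric reporting rule for vision ("Investigators are asked to report any loss in BCVA of ≥ 3 lines as a SAE") and states none for IOP. Concomitant medication tables are no substitute either: they are organised by drug class and name, and subjects may enter already taking one IOP-lowering drug.

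A reader might infer that the plan conceals pressure rises, or that the formulation choice would be wrong without the extra row. The documents support neither. Every crossing is flagged, and the choice draws on all safety and efficacy data through Month 6. Nor can one say that the table will lack an overall row, only that the text does not commit to one.

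**Conclusion.** The point holds as a cheap improvement. Each place that gives a time basis for the two threshold proportions says by visit, and by-visit rows do not determine the proportion of study eyes ever affected. No threshold-based cumulative proportion is planned in the text, although the variables are listed as primary and inform the formulation choice.

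The size depends on how long rises last, which the documents do not say. It is nil if all rises persist. In the 6-of-20 illustration the mean peak falls to 11% against 30% ever affected if each rise lasts one visit; this rests on uniform onset, seven visits and no missing data. A change of ranking is possible but imprecise at this sample size.

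**What to change.** Add to Table 14.3.18, by formulation for the randomized phase, the number and proportion of study eyes with (i) a rise from baseline of 10 mmHg or more and (ii) IOP of 30 mmHg or more at any post-treatment visit through Month 6, each with an exact 95% CI. Specify in SAP 15.2:

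- Initial-phase CF1 subjects are shown separately; they also have the extra Visit 3b.
- Unscheduled values are included, or shown as a second row.
- Any same-day post-injection values are shown separately, since raised IOP is also a named risk of the injection.
- Values after Month 6 are reported separately, because only subjects with residual implant attend those visits.
- Whether values after rescue therapy count.

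Keep the by-visit rows for timing. A count of eyes newly starting IOP-lowering drugs should not be part of this change: SAP 8.2.2 imputes many missing or partial start dates to the injection day, so a count of later starts would miss some.

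The cost is a few rows from data already collected. Reported IOP rates may look less favourable than single-visit figures, and intervals will be wide at about 20 eyes per group, so the rows should be labelled descriptive.

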4.3 Exclusion Criteria

Subjects meeting any of the following criteria during the screening or baseline evaluations will be excluded from entry into the study:

Ophthalmic:

1. Presence of a clinically significant epiretinal membrane, active retinal or optic disc neovascularization, active or history of choroidal neovascularization, presence of rubeosis iridis
2. History or presence of herpetic infection, toxoplasmosis, chorioretinopathy

3. Subjects with moderate non-proliferative diabetic retinopathy (as defined by the [International Clinical Diabetic Retinopathy Disease Severity Scale, 2002, in AAO PPP 2017](#)) or worse in either eye are excluded from participation
4. Any active infection
5. Aphakia, significant posterior capsule tear or iris trauma in the study eye
6. Anterior-chamber intraocular lens
7. Clinically significant media opacity
8. History of glaucoma or changes in the optic nerve head indicative of glaucomatous damage or visual field loss
9. Ocular hypertension in the study eye at qualification which is >23 mmHg without treatment or >21 mmHg if currently taking one IOP- lowering medication. Use of ≥ 2 IOP-lowering medications (fixed-dose combination therapies count as 2 medications) will exclude the subject
10. History of corticosteroid-induced IOP increase in either eye (defined as a documented increase of >10 mmHg following any previous initiation of steroid therapy, [Pleyer 2013](#))
11. Ocular condition in the study eye that, in the opinion of the investigator, would prevent a 15-letter improvement in visual acuity (e.g. severe macular ischemia).
12. Received an intraocular steroid injection or implant (e.g. via subconjunctival, or intravitreal routes of administration) within 6 months or any anti-VEGF treatment within 2 months prior to screening; Prior treatment with fluocinolone acetonide implant (e.g. RETISERT® or ILUVIEN®) or pan-retinal photocoagulation (PRP) would exclude the subject.
13. Intraocular surgery (including intraocular laser surgery), corneal refractive surgery or eyelid surgery within 3 months prior to Visit 1 or anticipated need for ocular surgery or ophthalmic laser treatment in the study eye during the study treatment period
14. Currently using topical corticosteroids in the vicinity of the eyes within the 1 month prior to Visit 1
15. Periocular depot of steroids placed within 6 months prior to Visit 2

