6.9 Concomitant Medication Assessments

Use of any medication – prescription or over-the-counter (OTC) should be recorded at the screening visit, and captured on the appropriate CRF, and the indication noted as part of the medical history. Treatments that are permitted to continue throughout the duration of the study will be recorded as concomitant medications at all subsequent visits. Judgment of continued study participation by the subject, and inclusion of this subject's subsequent visits in the safety and efficacy analysis will be made by the Investigator.

All medications which the subject has taken within 30 days prior to screening and during the study will be recorded in the CRF. The name of the drug, dose, route of administration,

duration of treatment and indication will be recorded for each medication. For combination products (e.g., CONTAC®), the brand name is required. For non-combination products, the generic name is preferred. The use of routine ophthalmic diagnostic pharmaceutical agents (e.g., fluorescein) will be allowed, and individual documentation not required. However, medications used as part of the intravitreal injection process other than topical or subconjunctival anesthetic and povidone iodine swabs (e.g. pre-or post-injection antibiotics or IOP-lowering medications) should be recorded on the CRF. Any change in dosing parameters should also be recorded in the CRF.

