11.2 Prior and Concomitant Medications

Prior and concomitant medications will be coded using World Health Organization (WHO) Drug Dictionary (WHODrug Global B3, September 2018) and summarized to the therapeutic drug class (Anatomical Therapeutic Chemical [ATC] 4 classification) and preferred name. If the ATC 4 classification is not provided, the next lowest classification that is provided in the coding dictionary will be used. The preferred name will be defined as the active ingredient; if the active ingredient is not provided or includes more than two ingredients (e.g., multivitamins), then the drug name will be summarized as the preferred name.

Concomitant medications are defined as those medications listed as having been taken (1) prior to initiation of study medication administration and continuing for any period of time following the first administration of study medication or (2) at any time following the first administration of study medication.

Prior and concomitant medications will be summarized for all subjects. Medications will be tabulated for each treatment group using frequencies and percentages. Subjects may have more than 1 medication per ATC text. At each level of subject summarization, a subject will be counted once if he/she reports 1 or more medications. Percentages will be based on the number of subjects in each treatment group. Listings of prior and concomitant medications will be generated for ocular and non-ocular data.

12. Implant Residual Assessment

Duration of implant visibility in days will be calculated as: (End Date - Date of Implant Injection) + 1, where the end date is defined as the latest date at which the implant is visible or date of implant injection for subjects whose implants are not visible at any of the follow up visits. Vitreous implant visualization will also be summarized at each visit by treatment group using categorical statistics. A subject listing will be provided for vitreous implant residual assessment.

13. Efficacy Analyses

The efficacy analyses will include the following:

- Percentage of subjects with ≥ 15 -letter improvement compared to baseline BCVA (assessed by ETDRS) at Month 6.
- Change from baseline in CRT as assessed by SD-OCT at Months 1, 2, 3, 4, 5, and 6
- Change from baseline BCVA letter score at Months 1, 2, 3, 4, 5, and 6
- Percentage of subjects with a ≥ 10 -letter improvement compared to baseline BCVA at Months 1, 2, 3, 4, 5, and 6

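### The primary IOP proportions use measured pressure whatever IOP-lowering treatment was given, and no planned table counts the study eyes that needed new treatment

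*SAP*

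**What the plan says.** SAP 2.1 lists IOP among the primary variables, with its change from baseline and both threshold proportions. SAP 15.2 Intraocular Pressure sets out the analysis: "Intraocular pressure will be summarized at each visit, using continuous and discrete summary statistics, including change from baseline", together with "the proportion of study eyes with an increase from baseline in IOP of 10 mmHg or more". A second proportion applies the 30 mmHg limit. For the listing it adds: "Increase from baseline in IOP of 10 mmHg or more or IOP of 30 mmHg or more will be flagged in the listing". Protocol 9.5 describes the same summaries. Neither section mentions IOP-lowering treatment.

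Such treatment is expected. Protocol 3.1 and the synopsis say: "In the case of elevated IOP or cataract, investigators should treat the subject according to standard practice". Protocol 5.6 leaves other necessary medication to the investigator, and Protocol 5.5 makes the trial open-label.

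Some use will not be a response to the implant. Exclusion criterion 9 (Protocol 4.3) excludes study-eye pressure above "23 mmHg without treatment or >21 mmHg if currently taking one IOP- lowering medication", so a subject may enter on one such drug. For drugs given around the injection, Protocol 6.9 states: "post-injection antibiotics or IOP-lowering medications) should be recorded on the CRF".

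On medication displays, SAP 11.2 says: "Prior and concomitant medications will be summarized for all subjects". Table 14.1.4.1 covers ocular prior and concomitant medications together, and Listing 16.2.4.5 gives them subject by subject. SAP 15.1 Adverse Events tabulates ocular TEAEs for the study eye.

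**The concern.** The stated case for AR-1105 is that a lower steroid dose may bring fewer steroid-related adverse events (Protocol 1 and 3.2). Protocol 6.8.4 names raised IOP among the events most often reported with the approved dexamethasone implant. Safety data through Month 6 will also help choose the formulation (Protocol 3.1).

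A proportion built on measured pressure describes pressure under care as given, which is the steroid effect less whatever treatment removed. Where treatment works, the error has one direction: pressure responses are under-counted.

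SAP 13.1 recognises the same problem for efficacy. There, rescue turns a subject into a failure, or replaces later values with the last one before rescue. The primary safety variable has no counterpart.

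**Working it through.** **Inputs from the documents.** 20 evaluable subjects per arm and 13.9% as the incidence ruled out when no event is seen (SAP 5). Thresholds of a 10 mmHg rise and 30 mmHg, assessed at each visit (SAP 15.2 Intraocular Pressure). The documents give no rate of IOP-lowering treatment and no expected rate of pressure events, so anything resting on those is a labelled assumption.

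**Step 1: the plan's own figure.** With 0 of 20 events, the one-sided 95% upper bound is 1 − 0.05^(1/20) = 13.9%. The figure is correct. It carries over to an IOP proportion of zero only if treatment cannot hide a true crossing.

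**Step 2: one eye through the definitions (illustrative readings).** Baseline is 16 mmHg and Month 1 is 25 mmHg; drops are then started and later readings are 17 mmHg.
- Rise at Month 1: 25 − 16 = 9, below 10; and 25 is below 30. Neither proportion counts the eye.
- Later rise: 17 − 16 = 1. Neither proportion counts it then either.
- The +9 does enter the Month 1 mean. Later means receive +1. Had the eye stayed at +9, a 20-eye mean would be (9 − 1)/20 = 0.4 mmHg higher.

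An eye that does cross, is treated and falls back is counted only at visits where it is above a limit. No any-visit proportion is defined.

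**Step 3: size per eye.** One eye is 1/20 = 5 points. Suppose k of 20 eyes start treatment without crossing, no other eye has an event, and the k eyes are counted. The upper bound is the 95th percentile of Beta(k + 1, 20 − k).

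| k | Proportion | One-sided 95% upper bound |
|---|---|---|
| 0 | 0% | 13.9% |
| 1 | 5% | 21.6% |
| 2 | 10% | 28.3% |
| 3 | 15% | 34.4% |
| 4 | 20% | 40.1% |

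**Step 4: how masking weakens a zero count.** Let p be the proportion of eyes that would cross if untreated, and m the share of those treated before crossing. Both are assumed. The chance that none of 20 eyes is flagged is (1 − p(1 − m))^20.

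| p | m = 0 | m = 25% | m = 50% | m = 75% |
|---|---|---|---|---|
| 13.9% | 5.0% | 11.1% | 23.7% | 49.3% |
| 20% | 1.2% | 3.9% | 12.2% | 35.8% |
| 30% | 0.1% | 0.6% | 3.9% | 21.0% |

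**Step 5: what the other planned outputs recover.**
- *TEAE tables:* they show the eye if the investigator reports the rise as an event. No visible rule makes a sub-threshold rise or a new drug an adverse event. The AE form records drug and non-drug action taken (Protocol 6.8.1), but no table in SAP 20 uses that field.
- *Ocular medication table:* it combines prior with concomitant use and counts subjects. Baseline therapy, injection-day prophylaxis and fellow-eye treatment (allowed by Protocol 5.6) are mixed with therapy for a study-eye rise.
- *IOP listing:* it shows every reading, but flags only the two thresholds.
- *Medication listing:* therapy can be traced by hand from the recorded drug, route, duration and indication (Protocol 6.9).
- *Procedures:* no table in SAP 20 counts IOP-lowering procedures.

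**The case against.** The strongest reply is that measured pressure under usual care is a legitimate descriptive summary in a small early-phase trial, and that it does not stand alone. Protocol 9.5 makes TEAEs the primary safety analysis, all adverse events are to be recorded regardless of cause, and no IOP threshold applies to them. A sub-threshold rise enters that visit's mean and the listing. With about 45 subjects, a reader can match the IOP and medication listings. All of that stands, and it is why the planned summaries should stay. It does not supply the missing number: how many study eyes on each formulation needed new pressure treatment.

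Some stronger readings are tempting and are not supported:
- *That a treated eye is reported as having no pressure effect.* This is true of the two proportions only, for the reasons just given.
- *That investigators may treat at will.* Protocol 3.1 refers to elevated IOP and standard practice. What is absent from the visible text is a numerical threshold.
- *That the pooled medication table is the only medication display.* Listing 16.2.4.5 is also planned.
- *That a definite number of points is lost.* If 15–30% of 20 eyes (3–6) started drops and half did so early, 1.5–3 eyes or 7.5–15 points would be affected. Neither rate is in the documents, and the sum assumes that every eye treated early would otherwise have crossed. An eye at +9 might have peaked there.
- *That the arms are treated differently.* Open-label care makes this possible; nothing in the documents shows it.

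**Conclusion.** The gap is real but limited. As written, the two primary IOP proportions and the later-visit means do not take account of IOP-lowering treatment, and they understate pressure response to the extent that such treatment is used and works. Each eye affected is worth 5 points at 20 per arm. The total cannot be estimated from the documents, and the tables of bounds and masking probabilities show sensitivity under assumed rates, not an expected bias. The existing outputs make the problem partly visible, so this is a cheap improvement rather than a flaw that invalidates the safety analysis.

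The conclusion rests on the visible text. Redacted footnotes and the Manual of Procedures were not available and are not counted as missing.

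**What to change.** In SAP 15.2 Intraocular Pressure, keep the planned measured-IOP summaries and add, by formulation:

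1. The number and percentage of study eyes, with exact CIs, that start, add or increase IOP-lowering medication, or have an IOP-lowering procedure, after injection day. Exclude prophylaxis given only on injection day and baseline therapy continued unchanged.
2. As a supportive descriptive summary with exact CIs, the proportion of study eyes with a rise of 10 mmHg or more at any visit, IOP of 30 mmHg or more at any visit, or treatment as in item 1.
3. A flag in the IOP listing for readings taken after such treatment began.

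Do not make the composite the basis for comparing formulations. It counts an unmasked decision to treat as an event, so it could import the differential treatment it is meant to reveal. Nor should the means be cut off at first treatment, because that removes eyes just as their pressure rises.

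The cost is a little programming and a check that the treated eye and any procedure can be identified in the CRF data; the medication fields listed in Protocol 6.9 do not name the eye. The reported IOP event rate may look less favourable. No clinical treatment rule changes.
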